Participant Withdrawal. A withdrawal occurs when an enrolled participant actively withdraws consent for further participation in the study, prior to completion of the protocol. Participants may withdraw consent from the trial at any time at their own request, or they may be withdrawn at any time at the discretion of the investigator for safety reasons. All attempts will be made to conduct all evaluations required by the protocol.

Addressing Negative Birth Outcomes. Preterm and negative birth outcomes are common in low income women, especially those with depression who smoke. We will handle these events in the following manner. Women who do not deliver live births will be allowed to continue postpartum treatment if they wish. We will remove them from the sample and replace them with a new participant. For women who experience preterm birth, we will consider providing additional sessions in the postpartum period to ensure a full treatment dose in these individuals. For women who experience other negative birth outcomes which interfere with participation in the postpartum period, we will attempt to make up for missed sessions by increasing the frequency of sessions within the postpartum treatment timeframe. Should negative birth outcomes cause an imbalance in treatment delivery across treatment conditions, this should be detected in our initial analyses of group differences, which will allow us to treat number of treatment sessions as a confounder if such differences are found to be correlated with outcomes (See Statistical Design and Power, Baysesian Modeling Strategy).

Prenatal.

During the prenatal period, participants of 18-22 weeks gestational age will receive 10 individual sessions of BA or HW. The prenatal HW treatment will be similar to the treatment that was utilized in our previous trial.⁵¹ These women will have 16 weeks to complete their 10 individual sessions.

During the prenatal period, participants of 23-32 weeks gestational age will receive 10 individual sessions of BA or HW. The prenatal HW treatment will be similar to the treatment that was utilized in our previous trial.⁵¹ These women will have 12 weeks to complete their 10 individual sessions.

We may do additional check in calls or text communications with participants to maintain engagement between prenatal and postpartum treatment sessions.

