A priori benchmarks for feasibility and acceptability will focus on retention at the 4.5-month postpartum assessment and completion of treatment visits. The study will be considered feasible if both the rate of retention at the 4.5-month postpartum assessment and average percentage of completed treatment sessions across subjects are 70% or above unless, in the case either rate is lower than 70%, we have convincing arguments that they can be improved sufficiently by modifying recruitment or intervention strategies. We will calculate statistics to estimate these feasibility parameters and calculate their 90% confidence intervals (CI), based on our sample size.

Adverse Event Monitoring & Concomitant Medication.

Adverse events and concomitant medications will be assessed throughout the study. Our procedures for assessing adverse events follow standard FDA and clinical practice guidelines and are well established in our research programs. Adverse event (AE) terminology and grades will be determined using the Common Terminology Criteria for Adverse Events (CTCAE), version 5.0, published by the U.S. Department of Health and Human Services. Only psychiatric adverse events, whether or not related to the treatment, will be reported. The counseling component will be overseen by PI [name].

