Adverse events will be reviewed by the PI and further reviewed by the medical team when appropriate. Adverse event monitoring will stop at the final treatment visit, or earlier if the ppt withdraws or becomes lost to follow up. Those AEs that are probably, possibly or definitely related to the treatment will be followed until resolution or end of study, whichever comes first. In the case of reports of suicidal ideation, depression or anxiety which we believe may be related to treatment, if possible, we will engage in our normal psychological assessments. This may not always be possible if reported by phone. In any case, procedures for Good Clinical Practice will be followed with respect to medical management of the symptoms. A specific plan for monitoring increased depression, anxiety, and suicidality is presented (Appendix. C-SSRS). The clinical assessment tools we use are the PHQ 9, GAD 7, and C-SSRS. The procedures are outlined (Appendix. Safety Monitoring Plan) apply to both symptoms of anxiety, depression, and suicidality. Treatment- emergent psychosis is extremely rare in smoking cessation trials. If it does occur, it will be captured by our assessment of adverse events. These cases will be referred for further evaluation by a Ph.D. Clinical Psychologist. The PI is responsible for determining the attribution of adverse events to the treatment.

Serious Adverse Event Reporting (SAE) Reporting

An adverse event or suspected adverse reaction is considered “serious” if, in the view of either the investigator or the sponsor, it results in any of the following outcomes:

- Death
- A life-threatening adverse drug experience – any adverse experience that places the patient, in the view of the initial reporter, at immediate risk of death from the adverse experience as it occurred. It does not include an adverse experience that, had it occurred in a more severe form, might have caused death.
- Inpatient hospitalization or prolongation of existing hospitalization
- A persistent or significant incapacity or substantial disruption of the ability to conduct normal life functions.
- A congenital anomaly/birth defect.

Important medical events that may not result in death, be life-threatening, or require hospitalization may be considered a serious adverse drug experience when, based upon appropriate medical judgment, they may jeopardize the patient or subject and may require medical or surgical intervention to prevent one of the outcomes listed in this definition.

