Examples of such medical events include allergic bronchospasm requiring intensive treatment in an emergency room or at home, blood dyscrasias or convulsions that do not result in inpatient hospitalization, or the development of drug dependency or drug abuse (21 CFR 312.32).

- Important medical events as defined above may also be considered serious adverse events. Any important medical event can and should be reported as an SAE if deemed appropriate by the Principal Investigator.

- All events occurring during the conduct of a protocol and meeting the definition of a SAE must be reported to the IRB in accordance with the timeframes and procedures outlined in "The University of Texas M. D. Anderson Cancer Center Institutional Review Board Policy for Investigators on Reporting Serious Unanticipated Adverse Events for Drugs and Devices".

- Serious adverse events will be captured from the time of the first protocol-specific intervention, until the last treatment visit, unless the participant withdraws consent. Serious adverse events must be followed until clinical recovery is complete and laboratory tests have returned to baseline, progression of the event has stabilized, or there has been acceptable resolution of the event.

It is the responsibility of the PI and the research team to ensure that serious adverse events are reported according to the Code of Federal Regulations, Good Clinical Practices, the protocol guidelines, the sponsor's guidelines, and Institutional Review Board policy.

STATISTICAL DESIGN AND POWER

We will employ a randomized, controlled between groups design in which 60 depressed pregnant smokers will be randomly assigned, using a form of adaptive randomization called minimization, to either Behavioral Activation (BA) or Health and Wellness (HW). We will stratify treatment assignment by baseline depression, smoking rate, and gestational age.

Data analyses will be conducted by our University of Texas Health Science Center collaborator [name]. [name] will be provided deidentified data from which to conduct the analyses and thus will not have access to participants' protected health information (PHI).

[figure not shown]
General Data Analytic Strategy: Bayesian Statistical Methods

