As outlined in the Safety Monitoring Protocol and Procedures (see Appendix), we will evaluating and assessing the severity of depressive and anxiety symptoms, other psychiatric disorders as well as suicide risk, using information from the PHQ-9, C-SSRS, and MINI administered at screening (AIM 1), and the PHQ-9, C-SSRS, MINI and Generalized Anxiety Disorder – 7 (GAD-7), administered at screening (AIM 3 & Aim 4). Additionally, we will be assessing for depressive and anxiety symptoms and suicide risk at the counseling sessions throughout treatment and have outlined procedures for monitoring changes of these symptoms and ideations (Appendix Safety Monitoring Plan). The document also outlines procedures for addressing other mental health concerns, reporting of elder or child abuse and neglect, domestic/intimate partner violence and crises that occur during sessions.

Participants who are rated on the Columbia-Suicide Severity Rating Scale at screening as having active suicidal ideation with some intent to act and active suicidal ideation with specific plan and intent, who fall within the extremely severe range of depressive symptom severity, who endorse having severe vegetative symptoms, bipolar symptoms, psychotic symptoms, or who are experiencing symptoms associated with Axis I disorders that place them at risk of harm will be further evaluated by a designated Master's or Ph.D. level Mental Health Professional (MHP) to make an appropriate treatment disposition. When needed, participants will be referred to collaborators at The University of Texas Health Science Center (UTH) to manage the action plan/treatment interventions as they deem appropriate or provided with outside referral(s).

Vulnerable Subjects

There is no additional risk to pregnant women and their fetuses posed by participation in the study. The intervention seeks to reduce smoking and depression in women in both the prenatal and postpartum period. Reduction in smoking and depression during these periods may benefit both the woman, the fetus and the neonate.

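### The psychiatric-only adverse-event rule makes no exception for serious events, conflicts as written with the SAE rule, and leaves birth outcomes without a reporting route

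*Combined protocol and SAP*

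**What the plan says.** Four parts of the protocol bear on this.

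- **Adverse Event Monitoring & Concomitant Medication.** Adverse events are assessed throughout the study, but "Only psychiatric adverse events, whether or not related to the treatment, will be reported". No exception is made for serious events.
- **Serious Adverse Event Reporting.** The definition has adverse events as its starting point ("An adverse event or suspected adverse reaction is considered") and makes seriousness a matter of judgment: the event qualifies when, "in the view of either the investigator or the sponsor, it results in any of the following outcomes". The list that follows includes death, "Inpatient hospitalization or prolongation of existing hospitalization" and "A congenital anomaly/birth defect". The section then requires: "All events occurring during the conduct of a protocol and meeting the definition of a SAE must be reported to the IRB". Capture runs from the first protocol-specific intervention to the last treatment visit, unless consent is withdrawn.
- **Addressing Negative Birth Outcomes.** "Preterm and negative birth outcomes are common in low income women, especially those with depression who smoke". The section then deals with make-up and additional sessions, and with removing and replacing women who do not have a live birth. It does not say how any of these outcomes is reported.
- **Vulnerable Subjects.** "There is no additional risk to pregnant women and their fetuses posed by participation in the study".

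The Aim 4 schedule (Table 2, prenatal and postpartum) has a column for birth and rows for adverse events and for the *Assessment of Changes since last visit* form. It has no row for birth outcome.

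**The concern.** The two reporting rules give different answers for one class of event: serious events that are not psychiatric. In most behavioral trials that class would be nearly empty. Here every Aim 4 participant is pregnant at entry, birth falls in the middle of treatment, and the protocol itself expects poor birth outcomes to be common. A member of staff who applies the psychiatric-only sentence as written would not report an event that the SAE section says must go to the IRB.

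The replacement rule adds to this. A woman whose pregnancy does not end in a live birth leaves the sample, so her outcome would not appear in the efficacy data either. At stake are compliance with the trial's own SAE rule, and the ability to support the statement on fetal and maternal risk with outcomes compared between the randomized groups.

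**Working it through.** The plan gives no figure to reproduce and no arithmetic applies. The check sets the rules side by side.

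1. **Scope of the adverse-event rule.** Psychiatric events are reported, related or not. The sentence has no qualifier such as non-serious. It restricts what is reported; the sentences before it still call for adverse events in general to be assessed.
2. **Relation of SAEs to adverse events.** The SAE definition starts from an adverse event or suspected adverse reaction and adds a seriousness condition. SAEs are therefore a subset of adverse events, and a limit placed on adverse events reaches SAEs on its face.
3. **Scope of the SAE rule.** All events that meet the definition go to the IRB, with no psychiatric limit.
4. **Where the rules disagree.** For a non-serious psychiatric event there is no conflict. For a psychiatric SAE both rules say report. For a serious non-psychiatric event the SAE rule says report and the adverse-event rule, read literally, says do not. A congenital anomaly is the clearest case: it is named as serious and is not psychiatric. An admission for an obstetric complication is another.
5. **Whether such events fall inside the capture window.** Aim 4 enrols at 18 to 32 weeks' gestation and delivers 10 prenatal sessions. After birth there is a break of up to a month, then 4 sessions over 6 weeks. Capture ends at the last treatment visit. Birth is therefore inside the window for any woman who resumes sessions. For a woman who does not resume, the last treatment visit may come before birth.
6. **Where a birth outcome would be recorded.** Table 2 names no such item. The treatment section says that participants are asked at each session about changes that include estimated delivery date and health. The form used for this is an appendix that is not supplied, so its fields are unknown.
7. **Tracing one case.** Take a stillbirth.
   - Under the literal adverse-event rule it is not psychiatric and is not reported.
   - Under the SAE list, death is named without saying whether fetal death is included, so its classification is left open.
   - Under Addressing Negative Birth Outcomes the woman is removed from the sample and replaced.
   - Under Table 2 no row captures the outcome.

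   Nothing written guarantees that this event appears in either the safety report or the analysed sample.

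**The case against.** The strongest reply is that the rules are compatible. The psychiatric-only sentence stands under a heading on routine adverse-event monitoring, and SAEs have their own section with an unrestricted duty to report. Read this way, birth defects and complication-related admissions are reported and the narrow limit applies only to ordinary events. That limit is a defensible choice for a behavioral intervention without study medication. The SAE section also defers to an institutional policy on serious unanticipated events, and a Safety Monitoring Plan appendix is cited. Neither is supplied, and either might settle part of the question. Staff must also learn of birth outcomes in order to apply the replacement and extra-session provisions.

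Much of this stands. The compatible reading is plausible and may well be what was intended. But it has to be inferred, and the definition of an SAE as a kind of adverse event works against it. The protocol describes the appendix as covering depression, anxiety, suicidality, other mental-health concerns, abuse and crises during sessions; birth outcomes are not mentioned. Learning of an outcome is also not the same as having a defined place to record and report it.

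A reader might go further and infer the following, which the documents do not support:

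- **Every hospital delivery is an SAE.** Seriousness applies only to something that is first an adverse event, and then in the investigator's or sponsor's view. An uncomplicated delivery need not be one.
- **Staff must choose between flooding the SAE reports with deliveries and omitting serious birth outcomes.** The compatible reading above is a third course.
- **Different sites will report differently and spoil the comparison of arms.** Treatment is remote, adverse events are reviewed by one principal investigator, and nothing suggests that interpretation would differ by arm. The analysis plan specifies no SAE table by arm.

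**Conclusion.** The point holds as a conflict between two written reporting rules, together with a missing route for birth outcomes. Read literally, the psychiatric-only sentence would leave all non-psychiatric SAEs unreported, against the SAE section's requirement. The reading that removes the conflict is reasonable but not stated.

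The size cannot be expressed as a count. The documents call negative birth outcomes common but give no rate, and preterm birth is not in itself on the list of serious outcomes, so any number of unreported events would be invented. It would also go too far to say that the no-additional-risk statement cannot be checked, because the fields of the changes form are unknown. What can be said is that the schedule names no birth-outcome item and the analysis plan no comparison of birth outcomes by arm.

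The conclusion rests on the text supplied; the Safety Monitoring Plan and the institutional policy could narrow it. The correction should be made because it concerns participant safety and is nearly free. The wording on delivery admissions would, alone, be only a clarification. Whether removal and replacement suits the efficacy analysis is a separate question.

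**What to change.** 1. In Adverse Event Monitoring & Concomitant Medication, state that the psychiatric-only limit applies to non-serious adverse events and that all SAEs are reported under the SAE section.
2. In the SAE section, state how admissions for delivery are classified, noting that an uncomplicated delivery need not be an adverse event under the existing definition. State also how fetal and neonatal death are classified.
3. In Addressing Negative Birth Outcomes, add a cross-reference to the reporting route.
4. Add a birth-outcome row to Table 2 at the first postpartum contact, recorded on the existing *Assessment of Changes since last visit* form. Suitable fields are live birth or not, gestational age at birth, neonatal death, congenital anomaly, and admission beyond the routine delivery stay.
5. Record the same outcome, where known, for women who are removed and replaced or who do not resume sessions, and tabulate it by randomized arm.

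The cost is protocol wording, a few extra fields at an existing contact, some effort to obtain outcomes for women who do not resume, and a small number of additional SAE reports. Clinical management is not affected.

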We will pay women in the Stage IB randomized trial up to \$25 for completion of the baseline screening visit, \$65 for completion of the end of prenatal treatment assessment, end of postpartum treatment assessment (2 ½ months) If the participant is lost to follow-up in either the prenatal or postpartum period or did not complete all visits during those timeframes, they will be compensated for the final visit that was completed. Given the variability in timing for each individual participant, if this scenario occurs payment may be delayed until the final visit is verified) and the 4 ½ months postpartum assessment, with the possibility of \$220 in total compensation.

Feasibility of Recruitment As indicated in [name] letter of support, the UT OB/GYN faculty provide clinical care at multiple clinics that will serve as recruitment sites for this study. A total of approximately 4,574 births per year to predominantly low-income women are under UT faculty care. Based on a study that was recently conducted in a UT clinic that is similar to clinics from which we will be recruiting, 14% of women identified as smokers.⁸⁹ A

study using a nationally representative survey found that among women who smoked cigarettes during pregnancy, 12.4% met criteria for a mood disorder and 37.3% of women with nicotine dependence had a mood disorder. Using the estimate of 14% smoking from the UT clinic study and national findings on percent of women with depressive disorders, we conservatively estimate that 25% of the 640 women who smoke will meet our depression criteria of scoring ≥ 10 on the Patient History Questionnaire 9 (PHQ-9) each year. Using these percentages, we estimate that 160 women would meet our criteria per year and that 50% would meet all eligibility criteria and consent to participate, providing around 80 women per year who would be eligible. Thus, we feel confident that we will be able to recruit up to 21 women who meet our eligibility criteria for Stage IA focus groups during year 1; up to 16 women for Stage IA pilot work during year 1 and early year 2, and; up to -50 women for Stage IB work during year 3.

Eligibility Criteria: AIM 4

Inclusion criteria for AIM 4

- 1) Meets criteria for current Major Depressive Disorder (MDD) as assessed by the Mini International Neuropsychiatric Interview (MINI) 7.0.2 OR PHQ score of 10 or greater.
- 2) ≥ 18 years of age
- 3) Have an address and telephone number where they may be reached

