the estimated frequencies, coupled with the low numbers in the control condition we chose to round any fraction for abstinence upward. This had the effect of producing a slightly higher effect in the control condition (n = 3 versus n = 2 abstinent) therefore rendering the simulated effect size more conservative). A fundamental difficulty is that the Frequentist approach cannot provide any indication regarding the relative probability of different values within the 95% Confidence Interval being the true parameter. The Bayesian estimate of the relative risk is slightly different (rounding was necessary in estimating the Frequentist but not the Bayesian solution), RR = 2.73, (95% CI: 0.90-11.44), however since these estimates are based on a posterior distribution it is possible to discuss the probability that an effect of a given magnitude is the governing parameter. Defining benefit as any RR > 1, the simulated posterior distribution shows that there is a 96% chance that the intervention confers this benefit and a more stringent definition (Relative Risk ≥ 1.50) is associated with an 85% probability that intervention confers

benefit. We stipulate that an intervention effect that has at least a 75% probability of increasing the relative risk of abstinence by >1.25 will warrant further investigation in a larger trial. While the above simulation provides a straight-forward example of how Bayesian modeling works, it is often necessary to use more sophisticated Bayesian approaches (e.g., logistic regression with Monte Carlo Markov Chain estimation methods). As such, final analyses will utilize Bayesian generalized linear modeling with multilevel-modeling for repeated measures data.

Bayesian Modeling Strategy Initial analyses examining group differences for baseline variables will use cross-tabulation, ANOVA's, and examination of correlations between baseline variables and specified outcomes. For the purposes of evaluating the comparability of groups, a posterior probability of $\geq 95\%$ will constitute evidence for statistically reliable differences. Baseline or demographic variables on which group differences are detected, and which are correlated with outcomes, meet the definition of confounders^{136, 137} and will result in two sets of analyses: one in which the relevant variable is included as a covariate and one in which it is not. This will permit determination of the degree to which any group differences might confound conclusions regarding treatment.

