
Broadly, the data analytic strategy will use generalized linear and multilevel models (SAS 9.4, R v. 3.5, and Stan 2.17) for both discrete (e.g. smoking abstinence) and continuous (e.g. depression) outcomes.¹³⁸⁻¹⁴⁰ Cross-sectional continuous (depression), dichotomous (smoking abstinence) and time-to-event (retention) data will be evaluated using generalized linear modeling or proportional hazards regression. All analyses will apply intention-to-treat principles with missing imputed as non-abstinent for smoking outcomes. For outcomes other than smoking, Bayesian approaches will implement joint modeling of observed outcomes and the missing data which is robust to ignorable missingness (i.e., MCAR and MAR).¹⁴¹ Sensitivity analyses will evaluate robustness of analytic conclusions to missing data. Non-ignorable missing data patterns will be addressed through pattern-mixture modeling methods.¹⁴² Convergence of Bayesian analyses on the posterior distributions via Monte-Carlo Markov chain (MCMC) will be assessed via graphical (Trace Plot, Autocorrelation Plot) and quantitative (Gelman-Rubin Diagnostics and Effective Sample Size) evidence. Evaluation of posterior distributions will permit statements regarding the probability that effects of varying magnitudes exist, given the data. Specification of diffuse, neutral priors will reflect the initial uncertainty regarding effect sizes. For all generalized linear models, priors for regression coefficients will be specified as \sim Normal ($\mu=0$, $\sigma^2=1 \times 10^4$), level one error variances will be specified as \sim Half-Normal ($\mu=0$, $\sigma^2=1 \times 10^4$). Choice of prior distribution for level two variances will follow Gelman's recommendations.¹⁴³ Bayesian Structural Equation Modeling (**BSEM**) prior specification will adapt recommendations from Muthén and Asparouhov.¹⁴⁴ Priors for the comparison of proportions will be specified as \sim Beta ($\alpha=1.0$, $\beta=1.0$).

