Conduct a preliminary randomized trial with depressed pregnant smokers comparing the BA to HW to evaluate the following: 1) The effect of BA on abstinence at 4 ½ months postpartum, which is a primary outcome. Logistic modeling will evaluate smoking abstinence, measured by biochemically verified TLFB, at 4 ½ months postpartum as a function of treatment group. **2) The effect of BA on depression at 4 ½ months postpartum, which is a primary outcome.** Generalized linear modeling will evaluate depression, measured by the PHQ-9, at 4 ½ months postpartum as a function of treatment group. **3) Feasibility of depressed pregnant smokers' acceptance of the smartphone delivery of BA and HW, and assessment components indicated by a) retention, which is a primary outcome, b) completion of prenatal and postpartum sessions, which is a primary outcome c) completion of study assessments, which is a secondary outcome d) strength of therapeutic alliance from both the participant and therapist perspective, which is a secondary outcome and e) participant and therapist ratings on satisfaction questionnaire, which is a secondary outcome.** Survival analysis will evaluate retention by modeling time to drop-out as a function of treatment condition. Binomial logistic modeling will evaluate the proportion of completed sessions as a function of treatment condition across the entire study as well as in the pre-natal and post-partum periods separately. Generalized linear models will evaluate participant and clinician measures of therapeutic alliance, measured by the WAI, as a function of treatment group. Similarly, generalized linear modeling will evaluate satisfaction as a function of treatment group. **4) Feasibility of study procedures as indicated by a) percentage of sessions interrupted by technical difficulties, which is a secondary outcome, and b) percentage of urine tests (cotinine and/or anabasine) received for biochemical verification of self-reported abstinence at 4 ½ months postpartum follow-up, which is a secondary outcome.** Binomial logistic models will evaluate the proportion of sessions interrupted for technical difficulties and the proportion of biochemically verified abstinence measures as a function of treatment. These analyses will provide estimates with 95% credible intervals for each of these proportions in each group that will permit assessment of feasibility.

Specific Analyses: Secondary Aim 1 (Stage IB)

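### The primary 4½-month PHQ-9 model names treatment group alone, and the only explicit rule for adding a baseline covariate would miss baseline PHQ-9 in about 90% or more of trials

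*Combined protocol and SAP*

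**What the plan says.** Under Specific Data Analyses: Aim 4, PHQ-9 at 4½ months postpartum is a primary outcome, and its model is: "Generalized linear modeling will evaluate depression, measured by the PHQ-9, at 4 ½ months postpartum as a function of treatment group". The Bayesian Modeling Strategy section treats the outcome as a single time point: "Cross-sectional continuous (depression), dichotomous (smoking abstinence) and time-to-event (retention) data will be evaluated using generalized linear modeling".

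On allocation, Statistical Design and Power says: "We will stratify treatment assignment by baseline depression, smoking rate, and gestational age". The method is minimisation, and the Aim 4 Design paragraph names the same three factors. Neither place defines the depression factor. Entry requires current major depressive disorder "as assessed by the Mini International Neuropsychiatric Interview (MINI) 7.0.2 OR PHQ score of 10 or greater", so the factor could be a score or a diagnosis.

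On baseline covariates, the Bayesian Modeling Strategy section sets a screen. A group difference counts at a posterior probability of at least 95%, and then: "Baseline or demographic variables on which group differences are detected, and which are correlated with outcomes, meet the definition of confounders". The consequence is two analyses, "one in which the relevant variable is included as a covariate and one in which it is not", with neither designated primary.

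More general statements say that "final analyses will utilize Bayesian generalized linear modeling with multilevel-modeling for repeated measures data" and that "the data analytic strategy will use generalized linear and multilevel models". Outcomes other than smoking are to be modelled jointly with the missing data. None of these says that baseline PHQ-9 enters the 4½-month comparison.

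**The concern.** A baseline covariate is worth including because it predicts the outcome, whether or not the arms happen to differ on it. A screen that starts from observed imbalance therefore selects on the wrong property. It is also least likely to fire for a variable that the allocation already balances.

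Three things follow. Baseline PHQ-9, already collected at screening, would usually be left out of the stated model. The factors used in allocation would be ignored in the analysis. If the screen did fire, two results for a primary outcome would exist with no rule for choosing between them.

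The trial is meant to supply effect sizes for designing later, larger trials, so the width of this interval matters. No decision threshold is set for PHQ-9, so the harm is confined to the effect estimate carried forward.

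**Working it through.** **Inputs from the documents.** The stated model term is treatment group. The screen threshold is 95%, with diffuse priors; regression coefficients have variance 1×10⁴ (SD 100), effectively flat. N is up to 50 in the Aim 4 Participants paragraph and 60 in Statistical Design and Power, so both were run. No PHQ-9 standard deviation, effect size or correlation is given.

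**The plan's own figure.** There is none for PHQ-9. The only worked example is abstinence at N=60 (7.6% v 25%), and it reproduces. The recomputed relative risk is 2.75 (0.90-11.47), against 2.73 (0.90-11.44) stated. P(RR>1) is 96.2%, P(RR≥1.5) is 84.9%, and Fisher p is 0.181.

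**Step 1: how often the screen fires.** With flat priors, a posterior probability of at least 95% in either direction is the same as |t| > t(0.95, N−2), a two-sided 10% test.

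- Simple randomisation: 10% by construction (simulated 9.6-10.0%).
- Minimising on a median split of PHQ-9 score: 1.0-1.6%.
- Minimising on a binary category with latent correlation 0.4-0.6 to PHQ-9 (N=50): 5.9-9.0%.

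The plan sets no threshold for the correlation condition. Tested at the same level, it lowers the two minimisation figures to 0.9-1.4% and 4.8-8.9%. The miss rate is thus about 90% or more on every reading.

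**Step 2: large-sample precision.** Adjusting for a covariate with correlation r to outcome multiplies the variance of the treatment effect by 1 − r²:

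- r=0.3: 0.91, so N=50 performs like 50/0.91 = 55.
- r=0.5: 0.75, so 50/0.75 = 67.
- r=0.7: 0.51, so 50/0.51 = 98.

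**Step 3: small-sample precision.** Simulation used 4,000 trials per cell, minimisation on three binary factors with an assumed 0.8 biased coin, and least squares. Entries are adjusted/unadjusted 95% interval width, for score-based / category-based minimisation (category at latent correlation 0.5).

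| Setting | r=0.3 | r=0.5 | r=0.7 |
|---|---|---|---|
| N=50, three covariates | 0.969 / 0.974 | 0.878 / 0.882 | 0.722 / 0.727 |
| N=50, PHQ-9 only | 0.959 / 0.964 | 0.868 / 0.873 | 0.714 / 0.720 |
| N=50, 30% missing, three covariates | 0.985 / 0.990 | 0.895 / 0.900 | 0.735 / 0.745 |
| N=50, 30% missing, PHQ-9 only | 0.963 / 0.967 | 0.874 / 0.879 | 0.718 / 0.729 |
| N=60, three covariates | 0.966 / 0.969 | 0.875 / 0.880 | 0.721 / 0.725 |
| N=50, three covariates, other two each 0.2 with outcome | 0.925 / 0.930 | 0.832 / 0.834 | 0.666 / 0.668 |

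Only the last row assumes that smoking rate and gestational age are prognostic. The 30% is the complement of the plan's 70% retention benchmark, taken as missing completely at random.

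In absolute terms, the unadjusted half-width at N=50 is t(0.975, 48) × √(2/25) = 2.011 × 0.283 = 0.57 SD. Multiplying by about 0.97, 0.88 and 0.725 gives 0.55, 0.50 and 0.41 SD.

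**Step 4: validity of the unadjusted interval (N=50).** Under score-based minimisation its coverage is 95.7%, 96.7% and 97.7% at r=0.3, 0.5 and 0.7, because the allocation removes variation that the model still counts. Under category-based minimisation it is 94.7-96.0%. Adjusted coverage is 94.1-95.3%.

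**The case against.** The Aim 4 text may not be a full list of model terms. It uses much the same phrase for therapeutic alliance, which is measured at seven visits and would need more than an arm term. PHQ-9 is collected at baseline and at every treatment visit, so the promised multilevel or joint models could carry the baseline score. This is a fair reading, and it makes the plan under-specified rather than firmly committed to an arm-only model. But no sentence applies that route to this outcome, and the section that promises multilevel models also calls depression cross-sectional. The other covariates the plan allows, sessions received and treatment started after enrolment, are post-baseline.

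The miss rate is not a measure of harm: any randomised baseline variable passes such a screen about 90% of the time, and the rarer firing under minimisation is the allocation doing its job. That is right. The miss rate shows only that the screen cannot be relied on to bring in the covariate; the loss is measured by interval width.

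The correlation is assumed and may be low. Entry at PHQ of 10 or more restricts range. With birth at 40 weeks, the gap from entry (18-32 weeks' gestation) to 4½ months postpartum (about 19.6 weeks) is roughly 28 to 42 weeks, with treatment in between. At 0.3 the gain is small. This stands.

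The 30%-missing rows are complete-case least squares, not the planned joint model, so they are indicative only. The two extra covariates also cost about 1 point of the gain, or about 2 with 30% missing, if they predict nothing. Both points stand, and neither removes the case for prespecifying baseline PHQ-9.

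**Conclusion.** The concern holds, as a point the plan should fix rather than one that invalidates the trial. As written, the primary PHQ-9 contrast is arm-only, and the one explicit rule for adding a baseline covariate would leave baseline PHQ-9 out in about 90% or more of trials. That rate follows from the rule and flat priors; the lower firing rates under minimisation depend on the assumed allocation details.

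The unadjusted comparison is unbiased. Its cost is an interval wider than the collected data require: the three-covariate model would be about 3%, 12% or 27-28% narrower at assumed correlations of 0.3, 0.5 and 0.7. The conclusion is the same at N=50 and N=60. Unadjusted intervals are noticeably conservative only if minimisation uses the PHQ-9 score itself. Confidence in the size is medium, because the documents give no correlation.

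**What to change.** In Specific Data Analyses: Aim 4, add baseline PHQ-9 as a continuous covariate, with smoking rate and gestational age, to the primary 4½-month PHQ-9 model whatever the observed balance. Name the adjusted treatment contrast as primary and the unadjusted contrast as supportive. In a linear model both target the same mean difference. Take these three variables out of the imbalance screen, which can stay for others. Define the depression factor used in minimisation, including whether it is a score or a diagnosis. If a repeated-measures model carrying baseline PHQ-9 is what is meant for this outcome, say so.

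The abstinence model should not be changed in the same way. At the plan's illustrative rates, N=50 yields 25 × 0.076 + 25 × 0.25 = 1.9 + 6.25, about 8 abstainers, too few for three more terms under very diffuse priors. Adjustment in a logistic model would also change the odds ratio being estimated.

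The cost is two or three sentences of wording. No new data, visits or participants are needed. The drawback is two degrees of freedom spent on covariates that may not be prognostic.
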